11.2 Data Handling

All study data will be managed by the DM-CRO. The overall procedures for quality assurance of clinical study data are described in the SOPs of the DM-CRO. The DM-CRO will prepare the DMP that will be approved by the Sponsor, prior to the start of the study, i.e., First Subject Screened. This document will describe, in detail, the procedures and processes related to data management.

All data of all subjects that are enrolled will be captured and stored in the study database. For screen failures, only the following information should be captured: date/time of ICF signature, date of birth, sex, race, AEs, date and reason for screen failure.

All data collected during the study is property of the Sponsor, irrespective of the location of the database and the DM-CRO.

The sponsor should ensure that the Investigator has control of and continuous access to the CRF data reported to the sponsor. The sponsor should not have exclusive control of those data.

The Investigator should have control of all essential documents and records generated by the Investigator/investigational site before, during and after the study.

Additional details are covered in the DMP.

11.2.1 Data Verification

The data will be verified as defined in the DMP and data validation plan (DVP). Data clarification forms (DCFs) will be issued to the investigational site for discrepant or missing data.

All changes to data will be captured in the database with a comprehensive audit trail.

Confidentiality Statement

2.0, Approved	Page 77 of 98
Clinical Study Protocol	Confidential
	Clinical Study Protocol 2.0, Approved

11.2.2 Coding

Adverse events, concomitant diseases, medical/surgical history, prior/concomitant medication will be classified according to the terminology of the latest version of the following dictionaries, at time of coding the first entry:

Adverse events, concomitant disease, medical/surgical history:	Medical (MedDRA	Dictionary ^{(®})	for	Regulatory	Activities
Prior/concomitant medication:	WHO [name]	ug Dictionar ic and Chemi	y Enl cal cla	nanced and A assification sy	Anatomical ystem

11.2.3 Database Lock

When all outstanding data management issues have been resolved and all validation, quality review and cleaning activities are complete as defined in the DMP, the Sponsor organizes a data review and ensures that the resolution of all raised queries and quality control of the changed data are performed by the CRO before approving the database locked.

Any changes to the database after that time can only be made by written agreement between the Sponsor and the data management and statistical teams at the CRO. Any changes must be documented in the database log file and if these impact the study analysis the PMP S.A. process for a database unlock may be requested.

The study database will be transformed into a Clinical Data Interchange Standards Consortium (CDISC) compliant format and transferred to the Sponsor as specified in the DMP and defined in the data transfer agreement. The clinical data will adhere to the CDISC Study Data Tabulation Model (SDTM) Data Structure Specifications.

Confidentiality Statement

12 PLANNED STATISTICAL METHODS

12.1 General Considerations

Full details of the statistical analysis will be described in the Statistical Analysis Plan (SAP). The following statistical analyses will not be performed prior to the finalization of the SAP. Any changes to the planned statistical methods will be documented in the SAP and CSR. The statistical evaluation will be performed using SAS®, version 9.2 or higher.

12.1.1 Stratification Criteria

The sample enrollment will enforce at least 25% of each sex, therefore demographics, baseline characteristics, PK and PD parameters analyses will be stratified by sex, as well as unstratified, as detailed in the SAP.

12.1.2 Definitions for Statistical Data Analysis

For PK and PD analyses, baseline will be defined as the last assessment prior to T_0 (5 minutes prior to T_0) for each study day of exposure.

Nicotine PK parameters (e.g., T_{max} , C_{max} , ...will be derived from background-corrected nicotine concentrations.

12.1.3 Descriptive Statistics

All data will be presented in listings, ordered by randomized sequence, subject, and time point unless otherwise specified.

Continuous endpoints will be summarized with descriptive statistics including number of subjects (n), number and percent of subjects with missing data, arithmetic means and standard deviations (mean and SD), median, first and third quartiles, minimum and maximum, and change from baseline.

For log normally distributed endpoints, geometric mean, geometric CV, confidence interval of the geometric mean, and percent change from baseline will be presented additionally.

Nominal categorical variables will be summarized by frequency statistics (number and percentage), including the number of missing data as a category.

Ordinal categorical data (e.g., T_{max}) will be summarized by number of subjects (n), number and percent of subjects with missing data, median, first and third quartiles, and minimum and maximum.

Confidentiality Statement

12.1.4 Handling of Missing Values and of Values outside the Detection Limits

In general, missing data will not be imputed in this study, due to the nature of the measurements and the short periods of exposure and use. However, for questionnaire data, total scores and domain or subscale scores may use a certain degree of imputation by averaging across individual item scores. Further details will be provided in the SAP.

Nicotine concentrations outside detection limits will be substituted using the following rules:

- BLOQ values before T_0 will be imputed by LLOQ/2.
- BLOQ values after the last quantifiable value are not included in the analysis (e.g., for the calculation of AUC).
- Any BLOQ value (after T₀ and before the last quantifiable value) would need to be queried and, if confirmed, it will be imputed by LLOQ/2.

Handling of missing answers to questionnaires will be described in the SAP.

12.2 Analysis Sets

The following analysis sets will be used for the data analyses.

12.2.1 Screened Population

The screened population consists of all subjects who underwent screening.

12.2.2 Safety population (SAF)

The safety population (SAF) will consist of all the subjects who signed ICF consent and have at least one exposure to NP 1.0 (including the product test with NP-1 at Admission regardless of whether or not they are enrolled in the study).

12.2.3 PK Population

The PK Population is a subset of the Safety population and consists of all randomized subjects for whom at least one nicotine PK parameter can be derived. Only subjects without major protocol deviations, as defined in the SAP, which have an impact on evaluability of the main objective will be included in the PK population.

Confidentiality Statement

12.3 Disposition of Subjects

Disposition of subjects will be summarized in the SAF population by reporting the number of subjects screened, enrolled, enrolled, and exposed to NP, randomized, completed, and discontinued the study with discontinuation reasons.

12.4 Protocol Deviations

Protocol deviations will be summarized in the SAF population by reporting the number and percent of subjects with protocol deviations, and the number of protocol deviations, will be summarized. Summarized Summarized by main deviation category (major/minor), sub-categories, and evaluability impact. Subjects will be counted once per deviation category and can be counted for more than one deviation category.

12.5 Demographics and Baseline Characteristics

Demographics and baseline characteristics will be summarized for the SAF and PK populations using the appropriate summary statistics as described in section 12.1.3.

Summaries will include sex, age, height, weight, BMI, nicotine/tobacco product use history, FTND, CYP2A6 activity and other endpoints that are only captured prior to product use.

12.6 Exploratory Analysis

12.6.1 Descriptive Statistics

Descriptive statistics will be performed on Background-Corrected Plasma Nicotine Concentrations, Observed Plasma Nicotine Concentrations, and PK, PD parameters in the PK population, by NP product and for all the planned timepoints, as described in section 12.1.3.

Summaries will be produced overall and stratified as described in section 12.1.1.

12.6.2 Primary Estimand Analysis

The primary estimand is defined as following:

Product Use Under Evaluation: 30 minutes product use period.

Target Population: Healthy adult smokers, who:

- Satisfy all inclusion/exclusion criteria (see section 5.1)
- Tolerate NP, based on a 30-minute product test at Admission (Day -1) after which subject have not, or have not been, discontinued.

Confidentiality Statement

Philip Morris Products S.A.	Clinical Study Protocol	Confidential
P5-PK-01-EXP	2.0, Approved	Page 81 of 98
D-1-4-14- OMC 0017599	P	

Variables of Interest: C_{max}, T_{max}, AUC_{0-5min}, AUC_{0-10min}, AUC_{0-15min}, AUC_{0-20min}, AUC_{0-25min}, AUC_{0-30min}, AUC_{0-35min}, AUC_{0-40min}, AUC_{0-1h}, AUC_{0-3h}, AUC_{0-6h}, AUC_{0-infinity}.

Intercurrent Events:

- Subject's non-adherence with 30 minutes (± 1 minute) IP use: If the subject uses other tobacco or nicotine product than the planned IP, or if the subject does not adhere with the planned IP use of 30 minutes (± 1 minute), the variables of interest from the related sequence's period will be set to missing and handled as MAR.
- Subject's non-adherence with abstinence periods: If the subject has used any nicotine or tobacco product during an abstinence period, the subject's variable of interest data from the related sequence's period will be set to missing and handled as MAR.
- Subject's discontinuation. The corresponding subject's variable of interest missing data will be handled as MAR.

Population-Level Summary Statistic:

- Geometric means ratios for C_{max}, AUC_{0-5min}, AUC_{0-10min}, AUC_{0-15min}, AUC_{0-20min}, AUC_{0-25min}, AUC_{0-30min}, AUC_{0-35min}, AUC_{0-40min}, AUC_{0-1h}, AUC_{0-3h}, AUC_{0-6h}, AUC_{0-infinity}.
- Median differences for T_{max}.

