6.2 Use of Investigational Product(s)

Subjects will not be forced to smoke cigarettes or use NP 1.0, Velo-NP and Zyn-NP and will be free to stop NP use at any time of the study.

Confidentiality Statement

Philip Morris Products S.A.	Clinical Study Protocol	Confidential
P5-PK-01-EXP	2.0, Approved	Page 44 of 98

During the screening period, subjects will be allowed to smoke and use tobacco/nicotinecontaining products according to their product use habits except during the procedures of the Screening Visit (section 9.1).

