6.2.4 Stopping Rules for Investigational Product

For safety purposes, using NP 1.0, Velo-NP or Zyn-NP should be temporarily stopped in the event of any signs suggesting nicotine overexposure, *e.g.*, gastrointestinal disturbance (nausea, vomiting, diarrhea, stomach or abdominal pain), cold sweats, headache, dizziness and breathing problems, or any reasons at the discretion of the Investigator.

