12.6.2.1 Main Analysis

Missing Data Strategy

The outcome data that will be missing or set to missing following an intercurrent event, will be assumed to be missing at random (MAR) and will be handled through model-based restricted maximum likelihood (REML) estimates.

Statistical Model

A mixed model analysis of variance (ANOVA) will be conducted on AUCs, and C_{max} endpoints in the natural logarithmic scale.

The model will include terms for sequence, period, product exposure as fixed effects and subject as a categorical random effect modeling the within subject correlations.

An heterogeneous Compound Symmetry matrix will be used to model the variancecovariance structure within subjects. If this model fails to converge, then the following variance-covariance matrix will be used (in this order) until one converges. Variance Components, Compound Symmetry, and finally no repeated statement.

Confidentiality Statement

Philip Morris Products S.A.	Clinical Study Protocol	Confidential
P5-PK-01-EXP	2.0, Approved	Page 82 of 98
Related to QMS-0017588		Document ID: VV-TMF-00821

The procedure will use the restricted maximum likelihood method and the Kenward-Roger method to compute the degrees of freedom.

The results of this analysis will be presented in terms of geometric least square mean ratios and 95% confidence intervals (95% CI) for the 4 respective variants of NP 1.0, Velo-NP and Zyn-NP ratios. The pairwise comparisons which will be performed are listed in Table 10.

	NP-2	NP-3	NP-4	Velo-NP	Zyn-NP
NP-1	X	X	x	X	X
NP-2		x	x	X	x
NP-3			x	x	x
NP-4				x	x

Table 10 List of pairwise comparisons

The model described above will be implemented in the SAS® language as:

```
PROC MIXED data=dataset method=reml;
    class Subject Sequence Period Product Sex;
    model Log(Parameter) = Sequence Period Product / ddfm=KR;
    repeated Product / subject=Subject type=csh;
    lsmeans Product / pdiff=LIST_OF_PAIRWISE_COMPARISONS cl;
PUN.
```

RUN;

The analysis of T_{max} will be performed by conducting a Wilcoxon signed rank test and calculating the median T_{max} for each product along with the Hodges-Lehmann estimate of the median difference between products, and the related 95% CI.

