4.2.1.1 Major Protocol Deviations

Subjects with major protocol deviations will be identified (at a population level) to determine whether they will be excluded from the PK population.

Major deviations will include but are not limited to the deviations presented in Table 4.1

Table 4.1 - Definition of Major Protocol Deviation Categories

Sub-Category	Description
Violation	Violation of inclusion/exclusion criteria
Mis-randomization	Violation of the product allocation process, including but not
	limited to the misclassification of subject's sex at randomization and incorrect product administered according to randomized sequence
Mis-use of product	Use of any nicotine or tobacco—containing product other than the assigned product during the exposure period or use of any nicotine tobacco-containing product during at least 10 hours of abstinence from any nicotine/tobacco containing products (nicotine wash-out).
	Product use not compliant with planned regimen of single product and 30 minutes product use period
Concomitant medications	Use of any drugs which are known to affect CYP2A6 activity

Among the eligibility criteria, violations of inclusion criteria 1, 2, 3, and 4 or of the exclusion criteria 2 and 14 will be considered as impacting the evaluability or integrity of the primary objective. Other major protocol deviations will be assessed for their impact on the evaluability of the primary objective during the pre-analysis data review meeting.

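### Any departure from 30-minute use deletes all 14 PK variables of that period, including partial AUCs already complete at pouch removal, and no planned analysis tests the missing-at-random assumption for the rest

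*Protocol*

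**What the plan says.** - **Rule.** Protocol 12.6.2 names departure from 30 ± 1 minutes of use as an intercurrent event, whatever its cause: "if the subject does not adhere with the planned IP use of 30 minutes", then "the variables of interest from the related sequence's period will be set to missing and handled as MAR". The listed variables are Cmax, Tmax and 12 AUCs, from AUC0-5min to AUC0-infinity. AUCs whose interval ended before the departure are not excepted.
- **Missing data.** Protocol 12.6.2.1 says the missing values "will be assumed to be missing at random (MAR) and will be handled through model-based restricted maximum likelihood (REML) estimates". SAP section 2 refers to protocol section 12 for the estimands, and SAP 6.4 rules out imputation of PK data. Tmax is analysed by signed rank test and Hodges-Lehmann estimate, outside the REML model.
- **Why use may stop early.** Protocol 6.2.4 says use "should be temporarily stopped in the event of any signs suggesting nicotine overexposure", or for other reasons at the investigator's discretion. Under Protocol 6.2 subjects "will be free to stop NP use at any time of the study".
- **Other planned analyses.** The sensitivity analysis (Protocol 12.6.2.2, SAP 6.5.2) deals with failed background correction. The PK supplementary analysis (Protocol 12.6.2.3, SAP 6.5.3) drops data with a high baseline concentration.
- **Analysis set.** Protocol 12.2.3 and SAP 4.1.3 both leave out of the PK population subjects whose major deviations affect evaluability. SAP Table 4.1 lists as major: "Product use not compliant with planned regimen of single product and 30 minutes product use period". SAP 4.2.1.1 names certain eligibility violations as affecting evaluability and sends the other major deviations to a pre-analysis data review.
- **Meaning of period.** The protocol synopsis and 4.1 describe 3 periods. Protocol 12.9.1 and SAP 3.1 describe 6.

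**The concern.** Two different things are deleted under one rule.

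The first is valid data. Plasma nicotine up to 20 minutes cannot depend on whether the pouch would have stayed in until 30. For a pouch removed at 20 minutes, AUC0-5min to AUC0-20min are therefore the values the estimand asks for. They need no hypothetical reasoning and no MAR assumption.

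The second is data that the estimand cannot use as observed: Cmax, Tmax and the AUCs running past removal. Here the question is whether MAR is credible. A stop prompted by signs of overexposure depends on exposure in that same use. Sequence, period, product and the subject's other uses explain that exposure only in part. Stops of this kind would selectively remove the high values of the affected product, and no planned analysis would show it.

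The wording also leaves open how much is lost. If 'period' means a day, one early removal could delete a compliant second use. If data review judged short use to affect evaluability, the whole subject would leave the PK population. SAP 4.1 uses that population for the PD endpoints too, so the subject's PES Aversion scores would go as well.

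**Working it through.** **1. Completed AUCs that are deleted.** The AUC end times are 5, 10, 15, 20, 25, 30, 35 and 40 minutes, 1, 3 and 6 hours, and infinity.

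| Removal (min) | AUCs already complete | Number of 12 |
|---|---|---|
| 10 | to 5, 10 | 2 |
| 15 | to 5, 10, 15 | 3 |
| 20 | to 5, 10, 15, 20 | 4 |
| 25 | to 5, 10, 15, 20, 25 | 5 |

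This does not depend on why the pouch came out.

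**2. The plan's own precision figure.** Inputs from Protocol 12.9.5: 24 subjects, GCV 40%, correlation ρ = 0.7, stated precision 15% or less.

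- SD of log Cmax = √ln(1 + 0.40²) = 0.3853.
- SD of a within-subject difference = 0.3853 × √(2 × 0.3) = 0.2984.
- 95% half-width, t with 23 df: 0.126 on the log scale, so the upper limit is 13.4% above the estimate. With z it is 12.7%; 10,000 simulated paired trials average 13.3%. The stated figure reproduces.
- With 22, 20 or 19 complete pairs the same calculation gives 14.2%, 15.0% or 15.5%.

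**3. Bias if removal depends on exposure.** The documents give no removal rate, so 5%, 10% and 20% of one product's uses are assumptions. The true ratio is 1.

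*Hard cut: the highest fraction f of one product's log exposures is lost.* With z the (1 − f) normal quantile and φ the normal density:

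- The unadjusted mean falls by 0.3853 × φ(z)/(1 − f).
- The five other uses explain 5ρ²/(1 + 4ρ) = 2.45/3.8 = 0.645 of the variance of the missing value. The MAR mixed model therefore leaves 1 − 0.645 = 0.355 of that fall.

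| f | Fall in unadjusted log mean | × 0.355 | Ratio, formula | Ratio, simulated REML | Unadjusted mean, simulated |
|---|---|---|---|---|---|
| 5% | 0.0418 | 0.0149 | 0.985 | 0.986 | 0.959 |
| 10% | 0.0751 | 0.0267 | 0.974 | 0.974 | 0.927 |
| 20% | 0.1348 | 0.0479 | 0.953 | 0.952 | 0.872 |

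The simulation used 4,000 subjects and six products, with a random-subject REML model without sequence or period terms.

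*Soft selection: probability of loss rises logistically with exposure, slope 1.5 per SD.* With realised loss of 4.4%, 11.5% and 19.3%, the REML ratio is 0.992, 0.983 and 0.969 of its full-data value.

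The unadjusted column matters only if the descriptive tables also set these values to missing. Protocol 12.6.2 states the rule for the estimand analysis.

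**4. Would a rerun on all observed data test MAR?** After early removal the observed Cmax is truncated. If a fraction f of one product's uses has Cmax cut by a proportion c, its mean log Cmax shifts by f × ln(1 − c). With f = 10%:

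- c = 20% (assumed): 0.10 × ln 0.8 = −0.0223, ratio 0.978.
- c = 30% (assumed): 0.10 × ln 0.7 = −0.0357, ratio 0.965.

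The MAR analysis under the hard cut gives 0.974. Both analyses are biased the same way by similar amounts, so their agreement would prove nothing.

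**The case against.** The strongest defence is that the estimand concerns 30 minutes of use. Values after early removal are truncated, so setting them to missing is a coherent choice. That stands for Cmax, Tmax and the later AUCs. It does not cover the AUCs already complete at removal.

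The second defence is size. No removal rate is given. Protocol 6.2.4 lists non-specific signs and speaks of a temporary stop without describing removal or its timing. Subjects unwilling or not ready to continue after a 30-minute NP-1 test leave before randomization, although NP-2 (pH 9.0) and Velo-NP (10 mg) are not tested beforehand. At low rates the REML bias is about 1%, and it partly cancels if both products compared are affected. The study is exploratory with no hypothesis. All this stands and limits the weight of the MAR point.

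Third, little is hidden. Concentrations are summarised by product and time point, and all data are listed. Tolerability is analysed in the safety population, with AEs leading to product discontinuation tabulated. That also stands, but none of it puts the lost AUCs back into the model.

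A reader might infer that the SAP contradicts the protocol by removing the whole subject where the protocol removes one period. The documents do not support that. Protocol 12.2.3 itself excludes subjects with major deviations as defined in the SAP, and in both documents exclusion depends on impact on evaluability. Whole-subject exclusion for short use is possible, not prescribed.

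**Conclusion.** The point holds in two parts of unequal strength.

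- **Certain from the text:** up to 5 of 12 AUCs that already equal their 30-minute-use values are discarded when a pouch comes out early, and no planned analysis recovers them.
- **Conditional:** if removals follow signs of overexposure, MAR is doubtful for the lost values. The affected product's ratio would then be biased downward by about 1–3% for roughly 5–20% removal under soft selection, and up to about 5% under a hard cut. This rests on GCV 40%, correlation 0.7, assumed removal rates and removal confined to one of the products compared. It is modest beside a CI half-width of about 13%, but nothing planned would detect it.

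A reader might infer that exposure to the strongest pouches will be understated. The documents do not establish this: they give neither the frequency of early removal nor evidence that it would concentrate in those products.

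**What to change.** All changes are to analysis and data capture; no clinical rule is touched.

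1. For early removal, retain every partial AUC whose end time is at or before the actual removal time. Set only Cmax, Tmax and later AUCs to missing, and report the number analysed per variable.
2. Confirm that the CRF captures the actual removal time and reason. The 30 ± 1 minute adherence check already needs the time, but the schedules in Protocol 9.3 to 9.5 list only collection of the used pouch.
3. Report the number and reasons of early removals by product.
4. If any occur, add a departure-from-MAR sensitivity analysis. One option is to raise the MAR-predicted log values of those uses by δ. Undoing the hard-cut bias above needs δ = 0.0149/0.05 = 0.30, 0.0267/0.10 = 0.27 or 0.0479/0.20 = 0.24, so a range of 0 to 0.30 would cover it. SAP 6.4 needs a stated exception if this is done by imputation. A run on all observed data can be shown, but only as a descriptive supplement.
5. State in SAP 4.1.3 and 4.2.1.1, consistently with Protocol 12.2.3, that short use affects only that product-use period and does not exclude the subject from the PK population.
6. Reconcile the 3-period and 6-period wording so that 'period' means one product use.

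The cost is SAP wording with a matching change to the rule in Protocol 12.6.2, a CRF check and possibly one added field, and one further analysis only if early removals occur.
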